1 STUDY OBJECTIVES

1.1 Primary Objective

To conduct a pilot randomized trial comparing outcomes of inguinal hernia surgery under local versus general anesthesia for adults aged 65 years and older. This will establish feasibility of conducting a multisite randomized trial and will optimize study procedures prior to conducting the multisite trial. We will measure

- (1) Rates of enrollment, percent of eligible patients enrolled, and reasons for non-enrollment
- (2) Proportion of participants completing all study visits
- (3) Proportion of missing data
- (4) Time to complete study evaluations and instruments
- (5) Participant satisfaction with study procedures and instruments
- (6) Whether survey instruments can be eliminated due to redundancy
- (7) Estimated sample size for a fully powered trial

We hypothesize that:

- (1) Based on our preliminary data, at least 75% of eligible patients will agree to be randomized.
- (2) We will be able to follow 100% of patients up to their 2 week postoperative visit (as essentially all patients keep this appointment in our clinical practice), and that we will be able to follow at least 90% of patients at the six month time point.
- (3) Missing data on study instruments will be <5%
- (4) Overall time burden for instrument completion will be acceptable to patients
- (5) One or more study instruments can be eliminated (thus reducing the time burden) because the other instruments may predict a substantial portion of variance
- (6) We will be able to use data from the pilot to estimate the necessary sample size for a multisite randomized trial

1.2 Secondary Objectives

Generate preliminary comparisons between the two study arms, to inform design of a larger multisite trial. Clinical outcomes that will be measured include:

- (1) Quality of life
- (2) Physical function
- (3) Cognitive function
- (4) Pain
- (5) Postoperative complications
- (6) Operative and anesthesia times
- (7) Recovery time (time spent in the post-anesthesia care and stepdown units)

We hypothesize that there will be sufficient data to estimate effect size (based on

means/medians and dispersion) for these key outcomes.

2 BACKGROUND AND RATIONALE

2.1 Background on Condition, Disease, or Other Primary Study Focus

Inguinal hernia repair - the most common general surgery operation in the U.S. - provides a unique opportunity to improve outcomes for older patients by changing surgical practice.¹ Nearly 80% of inguinal hernia operations are performed under general anesthesia versus 15%-20% using local anesthesia, despite the absence of evidence for superiority.^{2,3} The choice of anesthesia has particular implications for older adults because they face substantial short- and long-term risk of cognitive and physical decline after exposure to general anesthesia.^{4,5} Consequently, the American College of Surgeons and the American Geriatrics Society have identified a critical need in surgery: determining which operations have better outcomes when performed under local rather than general anesthesia.⁴

Currently, the evidence for choosing an anesthesia technique for inguinal hernia repair in older adults is inconclusive. Several small randomized trials and cohort studies have suggested that using local anesthesia for hernia repair reduces morbidity by one-third, unplanned admissions by 20%, and operative time and costs by 15%, while other studies showed no significant differences.^{2,6-8} However, there are significant flaws in these studies that severely limit their applicability to older adults: (1) They mainly focused on younger patients with limited comorbidity burden, largely ignoring individuals aged 65 years and older, (2) They did not adequately examine the effects of general anesthesia on cognitive function and quality of life for older adults and their caregivers. In particular, the only randomized trial that evaluated neurocognitive recovery evaluated a mostly younger population and did not look specifically at outcomes for older adults where the largest benefit is expected to occur.⁸ (3) They did not consult with stakeholders (patients, caregivers, physicians, hospitals, or health systems) to identify outcomes relevant to those groups. There is an urgent need to evaluate benefits of local anesthesia for inguinal hernia repair in older adults because the proportion of Americans age 65 and older is rapidly growing and will reach 20% of the population in the next 10 years.⁹ Improving postoperative recovery for patients having the most common general surgery operation in our country will have a tremendous effect on patient and caregiver quality of life.

2.2 Study Rationale

The study rationale is that prior to conducting a multisite randomized trial, it is necessary to identify relevant outcomes, understand barriers to greater use of local anesthesia, test study procedures, and confirm our ability to adequately recruit and randomly assign participants. Additionally, the proposed study will provide the applicant with critical training in the design, conduct, and analysis of clinical trials. This will uniquely position the applicant to change surgical care for older adults.

There have been two prior randomized clinical trials that compared local versus general anesthesia for inguinal hernia repair. Nordin et al. randomized 616 patients in Sweden to local,

regional, or general anesthesia.¹⁰ They did not specifically look at older patients but the mean age in each group was 56 years old. They found that the total operative time was five minutes faster for the local anesthesia group (90 versus 95 minutes) the incidence of postoperative pain requiring opioids and catheterization for urinary retention was decreased by 29% for the local compared to general anesthesia group and the rate of unplanned admission was decreased by 19%. A cost-effectiveness analysis conducted by the same group indicated that hospital costs were lower in the local anesthesia group (a difference of €311/\$378) and total healthcare costs were also lower (€316/\$384). A second trial from Scotland randomized 279 patients to local or general anesthesia, with a mean age of 55 years for both groups.⁸ This study did not find a significant difference in operative time, complications, length of stay, pain, or neurocognitive recovery as measured by a battery of tests. However, like the paper by Nordin et al., they did not specifically analyze outcomes in older patients which would tend to dilute the potential benefits of local anesthesia. Equally important, this study focused almost exclusively on healthy patients with smaller hernias, as evidenced by >90% of patients having an American Society of Anesthesiology score of 1 or 2 and a mean total surgical time of 48 minutes for each group (nearly 50% of operative time in the Nordin study).

There are several observational studies that compare outcomes from hernia repair under local or general anesthesia, and these mostly suggest that local anesthesia is associated with shorter operative time (5-10 minutes), fewer complications (1-3% reduction), and enhanced quality of life.^{2,11-15} However, only two of these studies look specifically at outcomes for older adults and both suffer from a poor approach to risk adjustment.^{11,12} Additionally, all the observational studies have a limited assessment of complications and failed to effectively evaluate rates of urinary retention and catheterization after surgery. Urinary retention is the most common complication of general anesthesia after hernia repair and results in considerable discomfort for patients who are catheterized to relieve it. Additionally, when patients do not resolve retention in a timely fashion, it results in the need for unplanned admission which increases hospital costs.⁶

The intervention chosen for testing in this study is the choice of anesthesia (local or general) for unilateral inguinal hernia repair. These are the primary methods of anesthesia for inguinal hernia surgery by most surgeons (though some perform the operation under spinal or regional anesthesia, this is rare). Both approaches are used in clinical practice with acceptable known risks and complications. General anesthesia is associated with risks of hypotension, venous thromboembolism, heart attack, stroke, pulmonary dysfunction, cognitive dysfunction, allergic reaction, and malignant hyperthermia. The main risks of local anesthesia include allergic reaction and hypotension (when the anesthetic is improperly injected into a blood vessel).

3 STUDY DESIGN

3.1 Summary & objectives

This will be a pilot randomized trial with two arms for patients having open unilateral inguinal hernia repair: (arm 1) local anesthesia versus (arm 2) general anesthesia. Each arm will recruit 40 patients.

The primary objective is to conduct a pilot randomized trial comparing outcomes of inguinal

hernia surgery under local versus general anesthesia for adults aged 65 years and older. This will demonstrate feasibility of conducting a multisite randomized trial and will optimize study procedures prior to conducting the multisite trial. The secondary objective is to generate preliminary comparisons between the two study arms, to inform design of a larger multisite trial.

The study design is illustrated in **Figure 1**.

3.2 Study population

The target population is patients aged 65 years and older who are having elective, open inguinal hernia surgery for initial, non-incarcerated, unilateral inguinal hernias.

3.3 Study location

The study will be conducted at general surgery clinics for 2 sites:

- (1) VA North Texas Healthcare System in Dallas, TX
- (2) Michael E DeBakey VA in Houston, TX

3.4 Duration of enrollment and follow up

Participants will be followed for a total of 6 months after surgery. For total study duration, recruitment will start 18 months after funding begins and will conclude after a total of 24 months of recruitment. Data collection will terminate 6 months after the last patient is enrolled.

3.5 Randomization and stratification

We will randomly assign older patients having inguinal hernia surgery to one of the two study arms: (1) local anesthesia or (2) general anesthesia. Our goal for enrollment will be 40 patients in

[figure not shown]

Figure 1. Overview of study design. Patients will be randomized to inguinal hernia surgery under either local or general anesthesia. We will collect baseline characteristics prior to surgery. Intraoperative and immediate postoperative outcomes include time, pain, and cognitive recovery. Post-discharge outcomes include pain, cognitive & physical function, and quality of life. All outcomes collected in-person unless otherwise noted

each arm, equally distributed by site. We will use a stratified randomization scheme with blocking within strata. Stratification factors include hospital location (Dallas or Houston) and age (65-75 or 75+ years). Equal allocation by strata will be used so that differences among hospitals and age groups will be balanced.

3.6 Blinding

Research assistants will be blinded to study assignment when conducting all assessments.

A description of the trial design should include:

- *Type/design of trial (e.g., placebo-controlled, double-mask, parallel design, open-label, dose escalation, dose-ranging)*
- *Specific statement of the primary and secondary outcomes (must be consistent with Study Objectives)*
- *Study population and groups/arms including sample size (including a table, if appropriate)*
- *Study location (e.g., in-patient or out-patient, clinic, community)*
- *Approximate duration of enrollment period and follow-up (specify individual participant vs. entire trial)*
- *Description of intervention and administration*
- *Randomization, blinding and any stratification*
- *Other protocol specific details, such as centralization of evaluations (e.g., central laboratory or central reading center for clinical scans)*

3.7 Study timeline

Table 1 (next page) outlines the study timeline. This includes completion of proposal aims 1 and 2, which will identify and prioritize study outcomes to supplement the list of measurements shown in section 6. Pre-trial data collection and analysis of interviews and focus groups will be completed by 18 months. We will then begin recruiting participants for the pilot randomized trial over a period of 24 months, allowing an additional 6 months for follow up of the last enrolled participant. In year 3, we anticipate beginning to write manuscripts and our R01 application based on the data from our pilot study. This will leave sufficient time to revise the grant in year 4 if the initial submission is not funded.

Table 1. Study timeline, including pre-trial activities (aims 1 and 2)

	Month 6	Month 12	Month 18	Month 24	Month 30	Month 36	Month 42	Month 48
Aims 1 and 2 (Pre-trial)								
Interviews to identify patient outcomes								
• Conduct interviews	X	X	X					
• Analyze data	X	X	X					
Focus groups to identify surgeon, anesthesia, & leadership outcomes								
• Conduct focus groups		X	X					
• Analyze data		X	X					
Prepare and publish manuscripts on qualitative data				X	X			
Aim 3 (Pilot trial)								
Recruit participants			X	X	X	X		
Complete follow up				X	X	X	X	
Analyze pilot outcomes			X	X	X	X	X	
Analyze clinical (secondary) outcomes							X	
Prepare and publish manuscripts on pilot data						X	X	X
Prepare, submit, and revise R01					X	X	X	X

4 SELECTION AND ENROLLMENT OF PARTICIPANTS

Key components of the success of a clinical study are the selection and enrollment of participants who are reasonably representative of the populations or characteristics under investigation to allow for sufficient generalizability. This section should define and describe the study population.

4.1 Inclusion Criteria

We will include patients who meet all of the following criteria:

1. Age \geq 65 years
2. Presenting to clinic with a unilateral inguinal hernia that is not incarcerated
3. Considered suitable for either general or local anesthesia
4. Willing to complete all study requirements, including follow-up continuing until six months after surgery

Provide a statement that participants must meet all of the inclusion criteria to participate in this study and then list each criterion. List as many criteria as necessary to clearly define your study population.

- *Demographic characteristics (e.g. gender, age) and the health state, presence or absence of a medical condition/disease.*
- *Required laboratory results, diagnostic methods, criteria for classification of current status, as measured within XX days prior to randomization. List specific tests and documentation methods.*

- *Prior therapy, if any. Consider listing specific prior treatments. Consider listing the allowable duration of prior therapy for the specific population to be studied (e.g., treatment-naïve, treatment-experienced or prior-treatment-failed “salvage” participants).*
- *Ability to understand study procedures and to comply with them for the entire length of the study.*
- *If men and women of reproductive capability will be enrolled, indicate whether contraception is necessary and required. If yes, include details of allowable contraception methods for trial.*

4.2 Exclusion Criteria

We will exclude patients who meet any of the following criteria:

1. The hernia that the patient is being evaluated for has undergone prior repair (ipsilateral recurrent hernia)
2. Any contraindications to general anesthesia (including malignant hyperthermia)
3. Allergies to local anesthesia
4. Evidence of hernia incarceration or bowel strangulation
5. Active local or systemic infection that would preclude the use of mesh for hernia repair
6. Need for concurrent surgical procedure at the time of hernia repair
7. English is not the patient’s primary language
8. Enrollment in other research studies

Patients with dementia or other cognitive dysfunction will not be excluded as long as there is a caregiver available to participate in the consent and follow-up procedures.

Provide a statement that all candidates meeting any of the exclusion criteria at baseline will be excluded from study participation and then list each criterion.

List as many criteria as necessary to clearly define your study population.

- *Specify health status or any clinical conditions (e.g., life expectancy, co-existing disease) or other characteristics that precludes appropriate diagnosis, treatment or follow-up in the trial.*
- *Clinical/laboratory indicators of current status, obtained within XX days prior to randomization. List the specific tests to be performed and the narrowest acceptable range of laboratory values for exclusion, consistent with disease and/or safety. Include as many as necessary.*
- *Specify any exclusion related to pregnancy, lactation, or plans to become pregnant. Specify methods for assessing current status and willingness to use contraception, if applicable. Include as many as necessary.*

- *Use of [excluded drugs, behavioral interventions, devices, etc.] within XX days prior to study entry. Treatment with another investigational drug or intervention (with time frame).*
- *For drug studies: allergy/sensitivity to study drugs or their ingredients.*
- *Cancer*
- *Current drug or alcohol use or dependence that, in the opinion of the site investigator, would interfere with adherence to study requirements.*
- *Inability or unwillingness of individual or legal guardian/representative to give written informed consent.*

4.3 Study Enrollment Procedures

4.3.1 Identification and recruitment

Each day, research assistants will screen the list of clinic appointments over the next 24-48 hours for general surgery clinics at both sites to identify patients referred for evaluation of inguinal hernias. Once potential participants are identified, research assistants will attend the clinic and wait for faculty surgeons to decide whether patients are candidates for inguinal hernia repair. If potential participants are deemed surgical candidates, then the research assistant will go with the faculty surgeon to confirm eligibility and to consent and enroll patients. At the clinic visit, the research assistants will explain the study purpose and procedures, and they will verify eligibility before attempting to recruit and consent patients. Information on all patients screened will be recorded in the study electronic database by the research assistants, who will also note reasons for ineligibility (no surgery scheduled, clinic appointment rescheduled, patient did not come to the clinic appointment, patient is enrolled in another study, etc). Similarly, a notation in the database will be made for all patients who are approached and the reasons for non-participation will be recorded (patient does not want to participate, patient specifically requests one type of anesthesia, patient was missed by the research assistant, etc.).

4.3.2 Consent procedures

The research assistants will bring a written informed consent to the clinic visit and review this with eligible patients. The conversation will include a discussion of the risks and benefits of local and general anesthesia, and a review of the existing evidence supporting the use of each technique in older adults. The consent form will also include discussions of costs, risks, benefits, alternative treatments, confidentiality, and study contact information. The consent will occur in the clinic room and in the presence of any caregivers who come to the visit. The research conversation will occur after the treating surgeon has evaluated the patient and deemed that individual a suitable candidate for hernia surgery and after the patient has accepted surgery as a treatment option. For individuals with dementia or other cognitive impairments, the consent will be conducted with the patient and caregiver. If no caregiver is present, then the patient will not be enrolled in the study. Additionally, the research assistant will emphasize to all patients that participation in the study is optional and deciding not to participate will not affect their clinical care. Patients will also be reassured that they can withdraw from the study at any time, and will

be provided a copy of the informed consent which contains contact information for the research team.

4.3.3 Enrollment of participants with cognitive impairment

Patients with known cognitive impairment or those identified by our baseline assessments will be included in the study. To optimize data collection, their identified caregivers will be asked to assist with completion of survey instruments and they will be contacted along with patients to prompt completion of all study visits. If caregivers assist with completion of any instruments, this will be noted in the research record.

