 - a. Measurement: At each visit, after completing all other study forms and procedures, participants will be asked to complete a brief 10-item Likert-type score to measure overall satisfaction with the study visit and a similar item assessing satisfaction with the time burden of the instruments. Additionally, we will conduct a brief interview with open-ended questions at the end of each visit asking patients to provide any feedback on the study procedures or instruments. These will not be recorded but field notes by the research assistant will be taken.
 - b. Timing: Assessments will occur at each study visit and will be reviewed at the last team meeting of each month.
 - 6) Outcome: Whether survey instruments can be eliminated due to redundancy
 - a. Measurement: To determine whether we can reduce the survey burden by eliminating redundant measures, we will employ methods outlined by Harrell for data reduction.²² Each survey instrument will be evaluated as the dependent variable in a separate linear regression with the scores of all other instruments used as predictors, along with demographic information. The adjusted R^2 (explained variance) for each regression will be estimated. Any instrument where the R^2 exceeds 40% will be eliminated based on the idea that little additional information is provided by including that instrument (i.e. the other surveys explain a substantial portion of the information contained within that instrument).
 - b. Timing: We will assess survey redundancy once 25% of planned enrollment is achieved and we will measure again at 75% enrollment. This will provide reasonable data stability for estimation and also provide time for us to test study procedures after eliminating any instruments that are found to be redundant.
 - 7) Outcome: Estimating sample size for fully powered trial
 - a. Measurement: For continuous variables, we will estimate means and standard deviations. For categorical variables, we will estimate proportions and 95% confidence intervals.
 - b. Timing: Final sample size estimate will be performed after data collection for the last patient is complete.

Table 2. Analysis of primary (pilot) outcomes		
Outcome	Measurement	Timing
Rate of enrollment and percent of eligible patients enrolled	
 Running count and graph of planned versus actual enrollment 	Team meeting (every other week)

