 - i. Confusion Assessment Method (CAM) short form: The CAM is the most widely used instrument for detection of delirium, with typical sensitivity of 94% and specificity of 89% across multiple studies.²⁶ The instrument is scored on a 7-point scale and we will consider a 0.5 standard deviation difference as the minimal clinically significant difference.²⁴ Items include evaluation of attention, disorganized thinking, and altered levels of consciousness.
 - ii. Montreal Cognitive Assessment (MoCA) 5-minute form: The MoCA is a widely used tool for detection of dementia and other cognitive impairment, and is sensitive when used as a global cognitive screening tool.²⁷ The 5-minute form was developed to (1) reduce the significant time burden of the longer version which typically takes 15 minutes to complete, while (2) maintaining the psychometric advantages of the longer form, and (3) facilitating assessment by

telephone rather than in-person interviews. The instrument evaluates memory/attention, language fluency, orientation, and recall. The 5-minute MoCA has strong correlation with the full version ($r=0.87$), maintains the discrimination of the full version (area under the curve 0.78 versus 0.75 for full version, $p>0.05$), and has strong test-retest validity (intraclass correlation coefficient 0.89).²⁷ Since the 5-minute MoCA was also developed for testing by phone or in person, it meshes with our protocol plans to conduct immediate and long-term follow up by phone. A difference of 3 points is typically considered clinically significant.²⁷

- iii. Trail Making Tests Parts A and B: The Trail Making Test is one of the most popular neuropsychological tests for detecting processing speed, attention, and visual scanning.²⁸ Part A requires participants to draw a line between circles containing numbers, and the circles must be connected in numerical order. Part B is similar, but alternates letters and numbers (1, A, 2, B, et). Both items are scored as time to completion and then normalized to population data based on age and education.²⁸ To address ceiling effects on Part B, we will use the efficiency score for individuals who do not complete the instrument in <300 seconds.²⁹ A 0.5 standard deviation difference in time is considered clinically significant.²⁸
 - b. Timing: All measures will be administered at baseline, prior to discharge, at 48 hours after discharge, at 2 weeks after surgery, and at 6 months after surgery
- 4) Outcome: Pain

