9.5 Data Analyses

9.5.1 Analysis of pilot/feasibility outcomes

We will use simple descriptive statistics (counts, ratios, mean/standard deviation, median/interquartile range, dispersion, proportions) to analyze the following outcomes: rate of enrollment and percent of eligible participants enrolled, reasons for non-enrollment, proportion of participants completing all visits, proportion of missing data, time to complete study evaluation and instruments, participant satisfaction.

To determine whether any study instruments are redundant and can be eliminated, we will run a series of linear regressions with one instrument score as the dependent variable and the other instruments and demographic variables as independent variables. This would take the form of the following, for example, where the Confusion Assessment Method (CAM) is the dependent variable for the first regression then becomes an independent variable for the second regression (and the FRAIL score becomes the dependent variable):

Regression 1: CAM =

$$\alpha + \beta_1 \text{demographics (age, comorbidity, gender, race, etc)} + \beta_2 \text{FRAIL} \\ + \beta_3 \text{Katz} + \beta_4 \text{MoCA} + \beta_5 \text{Trail Making} + \beta_6 \text{CERAD} + \beta_7 \text{Pain} \\ + \beta_8 \text{Carolinas Comfort Scale}$$

Regression 2: FRAIL =

$$\alpha + \beta_1 \text{demographics} + \beta_2 \text{CAM} + \beta_3 \text{Katz} + \beta_4 \text{MoCA} + \beta_5 \text{Trail Making} \\ + \beta_6 \text{CERAD} + \beta_7 \text{Pain} + \beta_8 \text{Carolinas Comfort Scale}$$

.
.

.

Additional regressions until all instruments have been tested

This process is repeated until all survey instruments have served as a dependent variable. We will calculate the adjusted R-squared for each regression, and this exceeds 40% (40% of the variance for that instrument is explained by the combination of participant demographics and other instruments), then that instrument is considered redundant and will be eliminated for future participants.²² Standard regression diagnostics will be used and we will consider fractional polynomial modeling of all continuous variables as previously described.³¹

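### Caregivers of cognitively impaired participants are asked to help with survey instruments, and nothing exempts MoCA, Trail Making or CAM or says how assisted scores are analysed

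*Combined protocol and SAP*

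**What the plan says.** Section 4.3.3 states that "Patients with known cognitive impairment or those identified by our baseline assessments will be included in the study". Section 4.2 likewise keeps patients with dementia eligible when a caregiver can take part. For these participants section 4.3.3 says that "their identified caregivers will be asked to assist with completion of survey instruments", with the aim of improving data collection. The only safeguard is that "If caregivers assist with completion of any instruments, this will be noted in the research record".

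The same term appears in the redundancy analysis. Section 9.4.1, item 6: "Each survey instrument will be evaluated as the dependent variable in a separate linear regression". Section 9.5.1 writes out the equations, "where the Confusion Assessment Method (CAM) is the dependent variable for the first regression", with MoCA and Trail Making as further terms beside Katz, pain and the Carolinas Comfort Scale (CCS). It adds: "This process is repeated until all survey instruments have served as a dependent variable".

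Section 9.4.2, item 3, describes MoCA as covering memory, attention, fluency, orientation and recall, and Trail Making as a timed line-drawing task done by the participant. On MoCA it says: "A difference of 3 points is typically considered clinically significant".

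**The concern.** MoCA and Trail Making are performance tests. A prompted recall item or a guided trail reflects patient and helper together. CAM is a less clear case, because section 9.4.2 presents it as a delirium-detection instrument, although its items on attention and disorganized thinking also depend on the patient's own responses.

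The battery is repeated in different settings: in clinic at baseline and at two weeks, in hospital before discharge, by phone at 48 hours, and by phone or video at six months (sections 6.2.2 to 6.2.4). A caregiver's presence and role may differ between these, and on the phone help may go unseen and so unrecorded. Help at one visit and not at the next could look like decline or recovery.

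Cognitive recovery is part of the central hypothesis (section 9.1.2). The pilot's means and standard deviations are meant to inform the size of the multisite trial (section 9.4.1, item 7), and the scores also feed the rule that drops instruments during the study (item 6).

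**Working it through.** The plan states no figure on this point, so there is none to reproduce. The check is of the text.

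**1. Does the request reach the cognitive tests?** Section 4.3.3 exempts no instrument, and its sentence on noting help refers to any instrument. Sections 9.4.1 and 9.5.1 apply the term survey instruments to every measure in the regressions, with CAM as the first dependent variable and MoCA and Trail Making in the same series. On the protocol's own usage, the request covers them.

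**2. Does another section exclude them?** Sections 6.2.2 to 6.2.4 say that research assistants administer a battery of tests. None says that the patient must work unaided or that a caregiver may not answer.

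**3. Does the analysis deal with assisted scores?**
- Section 9.5.1 uses instrument scores in the regressions without reference to the note.
- Section 9.5.2 compares continuous outcomes by Wilcoxon rank-sum test, with no subgroup analysis.
- Section 9.5.3 specifies complete-case analysis with multiple imputation as a check. An assisted score is not missing, so neither step removes it or tests its influence.

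**4. Which way does the plan lean?** Section 9.1.4 targets less than 5% missing data, section 9.4.1 (item 3) counts missing items by a single code, and no code is described for a test the patient cannot do unaided. Staff following the text have reason to accept an assisted score rather than a blank.

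**5. What size could it have?** Only a what-if is possible. Suppose a share f of participants is helped at one visit and not at the next, and help adds g points on MoCA. The mean change then shifts by f × g. Both values are assumptions. Taking f as 10% to 20% (8 to 16 of 80), and borrowing g = 3 from the protocol's threshold for a clinically significant difference:
- shift in mean change: 0.10 × 3 = 0.3 to 0.20 × 3 = 0.6 points;
- difference between arms: zero if help is balanced. With an assumed split of 4 versus 8 helped per 40, (8 − 4)/40 × 3 = 0.3 points;
- first redundancy check at 25% of enrolment: 0.25 × 80 = 20 patients, of whom 2 to 4 would have assisted scores.

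The 3 points is a threshold for importance and not an estimate of what help adds.

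**6. What would it cost to discard assisted scores?** Table 3 item counts: CCS 8, Katz 6, CAM 4, MoCA 8, Trail Making 2, pain 1, total 29. Cognitive items: 4 + 8 + 2 = 14. If all cognitive items of 10% to 20% of participants counted as missing, the rate at a visit with this full set would be 14/29 × 0.10 = 4.8% to 14/29 × 0.20 = 9.7%. This is an upper bound under the same assumed shares, against a target of less than 5%.

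**The case against.** The best defence is that the reading carries a term from the redundancy analysis into section 4.3.3. Where the protocol describes how the cognitive measures are given, it calls them tests administered by research assistants. Section 4.3.3 itself relies on baseline assessments to identify impairment, which presupposes that they measure the patient. Form-completion instructions sit in the Manual of Procedures (section 10.1), and staff practise every instrument on mock participants (section 10.3.1.2), so a rule on unaided testing may exist there. Help is also recorded, so assisted scores can be identified where the recording works.

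Much of this stands. It shows that help on MoCA may not be intended and that trained staff may refuse it. It does not remove the gap: the written request is broad, no exemption appears in the protocol, and no analysis uses the record.

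A reader might infer more: that the cognitive scores of all impaired participants are invalid, or that the arm comparison is biased by a known amount. The documents support neither. Harm arises only where help is actually given on a performance test. The share helped, the gain and the split between arms are all assumed, and the 0.3-point arm difference needs unequal help between arms and is one-tenth of the 3-point threshold. Variation between visits is possible but not documented. Section 6.2.3 expects family or caregivers to be assisting around discharge, so their absence from the recovery area cannot be taken for granted.

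**Conclusion.** The point holds as a gap in the rules for caregiver help and for analysing assisted scores. As written, section 4.3.3 asks for help on a class of instruments that the protocol elsewhere takes to include CAM, MoCA and Trail Making, and assisted scores would be analysed as ordinary data. The problem is clearest for MoCA and Trail Making.

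Its size is unknown. The what-if figures show that group-mean effects could be modest even when an individual's apparent change equals the protocol's own threshold. The between-arm comparison is exploratory and unpowered by design (sections 9.1.3 and 9.1.5), which limits the consequence. It should still be corrected before enrolment, because the change is cheap and a score obtained with help cannot be recovered afterwards. The conclusion rests on the protocol text alone; a rule in the Manual of Procedures would narrow it.

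**What to change.** **Section 4.3.3.** Limit caregiver help to visit reminders, logistics, and proxy or assisted report on the self-report instruments (Katz and CCS), flagged as such at each visit. State that MoCA, Trail Making and the patient-interview part of CAM are completed by the patient unaided, including at phone and video visits. Repeat this in the Manual of Procedures and in research assistant training.

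**Sections 9.1.4 and 9.4.1 (item 3).** Add a code of unable for a cognitive test the patient cannot do unaided, counted and reported separately from missing items under the target of less than 5%. Define it so that it does not overlap with the efficiency score that section 9.4.2 already gives for Trail Making Part B not completed within 300 seconds.

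**Section 9.5.2 or 9.5.3.** Prespecify a repeat of the cognitive comparison without any score flagged as assisted, as a sensitivity analysis. Outright exclusion from the main analysis is harder to defend: it would remove impaired patients, probably not at random, and could by itself use up or exceed the missing-data target.

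**Cost.** One paragraph, one code on the case report form and one sentence of analysis. The real downside is somewhat more unable entries among impaired patients, who would then be under-represented in the complete-case cognitive comparison. The count of such entries is itself useful feasibility information for the multisite trial.
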